12.6 Calculation or derivation of pharmacogenetic variables (Not applicable)

12.7 Calculation or derivation of health economics variables (Not applicable)

13. STATISTICAL METHODS AND SAMPLE SIZE DETERMINATION BY CRO

13.1 Description of analysis sets

The PK and PD analysis will be based on an as-treated approach (erroneously treated subjects, eg, those randomised to treatment A but actually given treatment B, will be accounted for in the actual treatment group). The PK analysis set will consist of all evaluable PK data appropriate for the analysis of interest. Correspondingly the PD analysis set will consist of all evaluable PD-data appropriate for the analysis of interest. Data affected by major protocol deviations or violations thought to significantly affect PK or PD of the drug will be excluded.

13.1.1 Analysis of Safety population

Safety analyses will be based on an as-treated approach (erroneously treated subjects, eg, those randomised to treatment A but actually given treatment B, will be accounted for in the actual treatment group) and based on the safety analysis set consisting of all subjects who received at least one dose of investigational product, and for whom any post-dose data are available. Post-dose data implies that there was contact during which an opportunity was given to report any health problem.

13.2 Methods of statistical analyses

Descriptive statistics includes n, mean, standard deviation (SD), min, median, and max, and for variables log transformed in the analysis, also geometric mean and coefficient of variation (CV).

13.2.1 Baseline characteristics

Baseline characteristics (age at consent, weight, height, BMI, race, HbA1c, fasting p-glucose, number of OADs and duration of T2DM) will be presented with descriptive statistics for all subjects.

13.2.2 Pharmacokinetics

All PK parameters derived for Day 5 and 8 (AUC_{0-24} , C_{max} , t_{max} , $t_{1/2}$ and CL/F for AZD1656 and AUC_{0-24} , C_{max} and t_{max} for AZ12555623) will be presented with individual values and descriptive statistics. All presentations will be done for both AZD1656 and AZ12555623.

13.2.3 Pharmacodynamics

For the PD efficacy variables (glucose after 20 min and time to reach 3.5 and 5 mmol/L) confidence intervals (95%) will be presented. A mixed model ANOVA with fixed effects for sequence, period and treatment and a random effect for subject within sequence will be used..

All PD-variables will be presented with individual values and descriptive statistics by treatment (with and without glucagon).

For mean values of the PD-variables by time will be presented graphically together in the same plot for with and without glucagon period.

13.2.4 Safety

AEs will be presented as number of patients with at least one AE, and will be further detailed by presenting the categories fatal AEs, serious non-fatal AEs and AEs leading to treatment discontinuation. All AEs should be summarized by the preferred term, assigned to the event using MedDRA vocabulary, for the periods on treatment, during follow-up and during study. Treatment period is defined as from date for start of study drug to date of last study drug or, when time is available, from time for start of study drug to 24:00 the date of last study drug or until the start of the next study drug if there are multiple exposures without a washout period. A follow-up period should capture any event occurring after the last treatment period up to the end of study for the patient, eg, the patient's last visit in the study. AEs will be represented in each period where there is overlapping occurrence.

Actual values and change from baseline for laboratory variables will be presented descriptively by treatment and time. Shift-tables will be used to classify the subjects in the categories below, within and above upper limit of normal (ULN), pre-treatment versus post-treatment. Pre-entry versus follow-up for laboratory variables will be presented in shift plots. A list with abnormal (out of reference range) laboratory values will be presented. For each abnormal value all values for that specific laboratory variable will be presented for the subject with the abnormal value. If a subject has more than one observation on the same measurement occasion, the results from the earliest draw should be used in all summaries.

Actual values and change from baseline for vital signs (BP, pulse and weight) will be presented descriptively by treatment and time.

All abnormal physical examination findings and ECG assessments will be listed. Any new or aggravated abnormal findings as compared to the baseline assessment will be listed.

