3.2 Secondary objectives

- To describe safety and tolerability of AZD1656 in T2DM patients
- To evaluate pharmacokinetic (PK) properties of AZD1656
- To assess the response in glucose, C-peptide and insulin during hypoglycemia in T2DM patients

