4.1.2 Rescue treatment – Low plasma glucose outside titration period

The following section applies during the residential period of the study (Visit 3), excluding 0-6 hours post dosing with AZD1656 on study Day 5 and 8.

If the subject experiences hypoglycaemic symptoms, a plasma glucose measurement should be obtained (before any treatment) and the subject should be treated according to local practice. For subjects with hypoglycaemia, defined as P Glucose <2.5 mmol/L (45 mg/dL), approximately 25 g glucose (juice) orally should be given as rescue treatment. Intravenous glucose could also be considered according to the judgement of the investigator.

If recurrent hypoglycaemia (defined as P-Glucose <2.5 mmol/L [45 mg/dL]), or hypoglycaemia that is difficult to cure, the subject should be discontinued from the study, Section 5.4.3.

If rescue treatment is needed during titration of investigational product (IP), the dose of AZD1656 should be reduced, see Figure 2. If rescue treatment is needed already after the initial dose the subject should be discontinued from the study.

Figure 1 Study design

[figure not shown]
[figure not shown]

Figure 2 Dose titration and glucose value

Note: the titration period is limited to Day 1 and Day 2 for each subject. On Day 3 the dose will be kept or reduced if needed.

Figure 3 Overview step wise hypoglycaemic clamp

[figure not shown]

Table 1 Study plan

| Event | Enrolment | Metfor- min treatment | Titration period | Maintenance period | Hypo- glycemic Clamp period 1 | Recovery period | Hypo- glycemic Clamp period 2 | Follow- up |
|--|--|-----------------------------|---------------------|-----------------------|--|--------------------|--|----------------------------------|
| Visit | 1 | 2 | 3 | 3 | 3 | 3 | 3 | 4 |
| Study Day | ≤28 days before rando- misation | Day -8 | D1-D2 | D3-D4 | D 5 | D 6-7 | D 8 | 7-10 days after Visit 3 |
| Informed consent | X | | | | | | | |
| Inclusion/exclusion criteria | X | | | | X | | | |
| Medical and surgical history including T2DM history | X | | | | | | | |
| Physical examination | X | | | | | | | X |
| Ophtamologic examination ^a | X | | | | | | | |
| Laboratory screening | X ^b | | X ^c | | X ^c | X ^c | X ^c | X |
| C-peptide, HbA1c & GAD antibodies | X | | | | | | | |

| Event | Enrolment | Metfor- min treatment | Titration period | Maintenance period | Hypo- glycemic Clamp period 1 | Recovery period | Hypo- glycemic Clamp period 2 | Follow- up |

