7.3.3 Recording of adverse events

AEs will be collected from the first administration of IP throughout the treatment period and including the follow-up period. AEs will be recorded during the study days at the investigational site and at the follow-up visit. Serious AEs will be recorded from the time when informed consent is obtained at the pre-entry visit until the follow-up visit.

Variables

The following variables will be recorded in the CRF for each AE: verbatim, date (time only during residential period) when the AE started and stopped, maximum intensity, whether the AE is serious or not, causality rating (Yes/No), action taken with regard to IP and outcome.

In addition, the following variables will be collected for all SAEs: Date AE met criteria for serious AE, Date Investigator aware of serious AE, AE is serious due to, Date of hospitalisation, Date of discharge, Probable cause of death, Date of death, Autopsy performed, Causality assessment in relation to Study procedure(s), Description of AE, Causality assessment in relation to Additional drug, Causality assessment in relation to Other medication.

The maximum intensity of each AE should be recorded and rated according to the following definitions:

- mild (awareness of sign or symptom, but easily tolerated)
- moderate (discomfort sufficient to cause interference with normal activities)
- severe (incapacitating, with inability to perform normal activities)

It is important to distinguish between serious and severe AEs. Severity is a measure of intensity whereas seriousness is defined by the criteria in Section 7.3.2. An AE of severe intensity need not necessarily be considered serious. For example, nausea that persists for several hours may be considered severe nausea, but not a SAE. On the other hand, a stroke that results in only a limited degree of disability may be considered a mild stroke but would be a SAE.

The Investigator will assess causal relationship between IP and AEs, and answer “yes” or “no” to the question “Do you consider that there is a reasonable possibility that the event may have been caused by the investigational product.

Causal relationship in cases where the disease under study has deteriorated due to lack of effect will be classified as no reasonable possibility.

For SAEs causal relationship will also be assessed for other medication and study procedure. Note that for SAEs that could be associated with any study procedure the causal relationship is implied as “yes”.

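### The on-treatment AE summary pools ordinary AZD1656 dosing with two induced hypoglycaemias and a glucagon injection, and Sections 13.1.1 and 13.2.4 leave the grouping of AEs unreconciled

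*Protocol*

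**What the plan says.** The AE table serves a secondary objective in Section 3.2: "To describe safety and tolerability of AZD1656 in T2DM patients".

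Section 13.2.4 names three summary periods: "All AEs should be summarized by the preferred term, assigned to the event using MedDRA vocabulary, for the periods on treatment, during follow-up" and the whole study. It defines the first as follows: "Treatment period is defined as from date for start of study drug to date of last study drug". Where clock time is available, the period may instead run to midnight of the last dosing date or "until the start of the next study drug if there are multiple exposures without a washout period".

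For laboratory variables and vital signs, the same section asks for summaries by treatment and time. It asks for no such split of AEs. Section 13.1.1 bases the safety analyses on treatment actually received and uses treatments A (glucagon) and B (control) as its example.

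Section 7.3.3 records for each AE "date (time only during residential period) when the AE started and stopped", with a yes/no answer on causality to the investigational product. It adds: "For SAEs causal relationship will also be assessed for other medication and study procedure".

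**The concern.** The on-treatment period covers quite different conditions. On most days subjects take AZD1656 twice daily with food. On Days 5 and 8 they take the full daily dose at once after an overnight fast and are clamped to a target nadir of 2.7 mmol/L, with insulin as needed. At 3 h on one of those two days they receive 1 mg glucagon.

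Symptoms provoked by the clamp or the injection enter the same row as events under ordinary dosing. A reader who takes that row as the tolerability profile of AZD1656 cannot tell the sources apart. Because Section 13.1.1 points to an A/B grouping that 13.2.4 does not carry through for AEs, two programmers could build different tables and each claim to follow the protocol.

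**Working it through.** The plan states no figure to reproduce. The check compares the AE period definition with the dosing schedule and then asks what the pooled count can identify.

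**Schedule against definition**

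- AZD1656 is the only investigational product listed (Section 6.4.1). It is given for 8 days (synopsis) and continues on the recovery Days 6 and 7 (Section 4.1), so there is no washout between the clamps.
- First to last study drug is therefore one window holding titration, maintenance, recovery, both clamps and the one glucagon injection per subject.
- Clamp days are 2 of 8 (25%). The two 0-6 h windows are 12 of 8 × 24 = 192 h (6.25%). These are shares of time only and do not enter a per-subject AE proportion.

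**Does the next-study-drug clause separate the conditions?** The protocol does not say what counts as the next study drug here.

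- If it means AZD1656, the clause leaves one window or cuts at every dose.
- If it means glucagon, the control clamp has no drug start to open a period.
- If it means the A and B periods, events on Days 6 and 7 under twice-daily dosing would fall to whichever of A or B came first.

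None of these readings separates clamp from non-clamp events.

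**Do provoked symptoms reach the table?** Under Section 7.3.3 a low protocol-mandated glucose value alone is an AE only if it is serious or the reason for stopping the product. Accompanying symptoms are AEs, and no exemption is stated for clamp symptoms.

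**What the pooled count can identify.** Let q be the probability that a subject has an AE outside the clamps and h the probability per clamp. Both are assumptions; the documents give neither. With independence:

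P(at least one AE on treatment) = 1 − (1 − q)(1 − h)²

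| q | h = 0.1 | h = 0.3 | h = 0.5 | h = 0.7 |
|---|---|---|---|---|
| 0.10 | 0.27 | 0.56 | 0.78 | 0.92 |
| 0.30 | 0.43 | 0.66 | 0.83 | 0.94 |

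In reverse, fix the pooled proportion at 0.60 (6 of the 10 randomised), so that h = 1 − √(0.40/(1 − q)):

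- q = 0: h = 1 − √0.40 = 0.37
- q = 0.2: h = 1 − √0.50 = 0.29
- q = 0.6: h = 1 − √1 = 0

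The same pooled result fits an event probability outside the clamps of 0, 20% or 60%. This shows that the pooled count does not identify q. It does not predict what the trial will see.

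**The case against.** The strongest reply is that segmenting a descriptive AE table is commonly left to the SAP, which Section 13.3 says is still to come, and that 13.2.4 forbids no further split. With onset times recorded, nothing needed for the split is lost. That stands, and it limits the point to the grouping that the protocol itself states and leaves unreconciled.

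A second reply is that causality is already handled. Appendix B tells the investigator to weigh other drugs and allows a no where another cause is more likely, so an event plainly due to glucagon or infused insulin need not be attributed to AZD1656. This also largely stands. What remains is that ambiguous cases default to yes and that procedure and other medication are asked about only for SAEs.

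A third reply is that the clamp is not separate from the drug. Section 3.1 describes the hypoglycaemia as induced by a single dose of AZD1656, and insulin is a supplement. The 0-6 h windows follow the full daily dose given at once, with peak concentration within 1 hour (Section 2.1). This stands in full. A reader might infer that tolerability should be judged only on the days outside the clamps, but that would drop the hours after the largest single doses.

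Finally, Section 4.1.2 limits its rescue rules to the residential period "excluding 0-6 hours post dosing with AZD1656 on study Day 5 and 8". That marks the window as a distinct condition in conduct. It does not define an AE analysis period.

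**Conclusion.** The point holds as one of presentation and consistency on a descriptive secondary objective. On its plain reading, 13.2.4 gives one on-treatment AE row that mixes ordinary dosing with two induced hypoglycaemias and a glucagon injection. Neither the next-study-drug clause nor the A/B basis in 13.1.1 resolves this. The pooled count alone does not show which AEs arose outside the challenge procedure.

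Two stronger readings are not supported. A reader might infer that the table will overstate AZD1656 events by some large factor, but the documents give no event rates, so any such factor rests on assumed inputs. A reader might also infer that tolerability is lost for good, but start times during the residential stay allow the split later.

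A split would still not give a controlled estimate, because no treated period is free of AZD1656. The primary analysis and sample size are untouched.

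**What to change.** In Section 13.2.4, keep the overall on-treatment summary and add AE counts by time of onset, shown side by side:

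- (a) AZD1656 dosing outside the clamp windows: Days 1-4, Days 6-7, and after 6 h on Days 5 and 8
- (b) the glucagon clamp, 0-6 h, split at the 3 h injection
- (c) the control clamp, 0-6 h, split at the same time
- (d) follow-up

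The cut at 3 h keeps events before the injection apart from those after it and gives the control day a matching comparison. In the added table, count each event once, by its start, because the section's rule for overlapping events would otherwise repeat it across segments. Glucagon effects that begin after 6 h would fall in (a); a footnote can say so.

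Align Section 13.1.1 with this grouping. Do not rest the AZD1656 tolerability statement on (a) alone, since (b) and (c) contain the full daily dose given as a single fasting dose.

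Optionally, record causality to procedure and other medication for non-serious AEs with onset in (b) or (c). This is the one element that cannot be added from the recorded onset times.

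The cost is a short text change, a slightly longer table with small counts per cell and, if the option is taken, one more CRF item.

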4.1.1 Titration procedure

The dose of AZD1656 will be individually titrated stepwise provided that the glucose values of the subject are within acceptable limits. The decision to increase the dose on study Day 2 (dose titration) and the decision to continue on the individual tolerated dose on study Day 3-4 will be based on the morning fasting glucose on the actual day and the post-prandial glucose values from the previous day ([Figure 2](#)). After Day 2 no further dose increases are allowed, but down-titration to 40 mg bid may be needed. Study specific discontinuation criteria applies for hypoglycaemia or pronounced hyperglycaemia as described in [Section 5.4.3](#).

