| 0230 | X | | | X | | |
| 0245 | X | | | | | |
| 0300 | X | | | X | | Clamp release and Glucagon injection |
| 0315 | | | | X | | |
| 0320 | | | | X | | |
| 0330 | X | | | X | | |
| 0345 | | | | X | | |
| 0400 | X | | | X | 6 | Reversed clamp ^a |
| 0430 | X | | | X | | Meal ^b |
| 0500 | X | | | X | | Normalised P-glucose ^c |
| 0600 | X | | | X | | Stop telemetry |
| 1200 | | X | | | 7 | |
| 2400 | | | | X | 8 | |

- a Minimal Plasma glucose value increased from 2.7 to 3.2 mmol/L.
b Minimal plasma glucose value increased from 3.2 to 4.0 mmol/L.
c Minimal plasma glucose value increased from 4.0 to ≥ 5.0 mmol/L.

Table 3 Time schedule during Day 1, 2, 3, 4, 6, 7 and 9^a

| Protocol Time | Glucose sampling (bedside) | ECG/ BP/ Pulse | Safety lab screen | Other |
|---------------|----------------------------|----------------|-------------------|---------------------------------|
| Pre-dose | X | X ^b | X ^c | |
| 0000 | | | | Adm of IP followed by breakfast |
| 0200 | X | | | Snacks |
| 0400 | X | | | Lunch |
| 0600 | X | | | Snacks |
| 0900 | X | | | Adm of IP followed by dinner |
| 1200 | X | | | Evening meal |
| 1400 | X | | | At bedtime |

^a Day 9 only includes pre dose safety lab screen and one glucose sampling after breakfast, thereafter discharge from clinic.

^b Only on Day 1, 4 and 7

^c Only on Day 1, 6 and 9

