5.4.3 Study specific criteria for discontinuation

Events of hypoglycaemia (defined as plasma glucose <2.5 mmol/L (45 mg/dL), at 2 occasions or 1 event of hypoglycaemia that is difficult to cure despite glucose administration (according to the judgement of the investigator) or prolonged hyperglycaemia (defined as 2 consecutive days with fasting morning plasma glucose >15 mmol/L (270 mg/dL) should lead to discontinuation of treatment and the event should be reported as AE.

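### The on-treatment adverse event period ends at midnight on the last dosing date, so an event starting in the hours after a final dose is counted as follow-up only

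*Protocol*

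**What the plan says.** Protocol Section 13.2.4 summarises AEs for three spans: on treatment, follow-up and the whole study. Where clock times exist, the on-treatment span runs "from time for start of study drug to 24:00 the date of last study drug". It has one extension, "or until the start of the next study drug if there are multiple exposures without a washout period". After that, "A follow-up period should capture any event occurring after the last treatment period up to the end of study for the patient". For events that straddle a boundary, "AEs will be represented in each period where there is overlapping occurrence".

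The clock-time version of the rule applies in the clinic, because Section 7.3.3 records "date (time only during residential period) when the AE started and stopped".

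Four other places bear on the point:

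- **Table 3 (in Section 4.1.2).** On twice-daily days the second dose comes 9 h after the first: "Adm of IP followed by dinner". On Days 5 and 8 there is a single morning dose (Section 6.4.2).
- **Section 4.1.1.** The dose decision on Days 2 to 4 "will be based on the morning fasting glucose on the actual day", together with the previous day's post-prandial values.
- **Section 5.4.3.** Treatment stops for hypoglycaemia below 2.5 mmol/L on two occasions, for one hypoglycaemia that is difficult to cure, or for hyperglycaemia on "2 consecutive days with fasting morning plasma glucose >15 mmol/L". Such an event is to be reported as an AE.
- **Section 2.1.** The half-life of AZD1656 is about 3-4 h. Its active metabolite has a slower terminal phase, with no figure given, and mean exposure of about 20% of the parent.

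**The concern.** The cut is set by the calendar, not by exposure. A subject whose last dose was taken with dinner has only the rest of that evening counted as on treatment. If hypoglycaemia then starts overnight, or is found at the pre-dose reading, and dosing is not resumed, the date of last dose is the day before and the event falls after the cut.

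Neither safeguard in Section 13.2.4 helps. The next-dose extension needs a next dose. The overlap sentence needs an event that spans midnight, not one that starts after it.

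Describing the safety and tolerability of AZD1656 is a secondary objective (Section 3.2), and hypoglycaemia is a named reason for stopping. An event that begins while drug is still present, and that ends treatment, would be tabulated under follow-up and be absent from the on-treatment column.

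**Working it through.** There is no figure in the plan to reproduce. The check is one of timing.

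**Inputs.** The second dose is 9 h after the first (Table 3). The half-life is 3-4 h (Section 2.1). The protocol gives no clock time for dosing, so a morning dose at 07:00-09:00 is an assumption; it puts the evening dose at 16:00-18:00.

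**Formula.** Fraction of parent drug remaining = 0.5^(hours since dose / half-life). This treats decline as single-exponential from the time of dosing and ignores anything left from the morning dose.

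| Morning dose (assumed) | Evening dose to 24:00 | Remaining, half-life 3 h / 4 h | Day 8 dose to 24:00 | Remaining, half-life 3 h / 4 h |
|---|---|---|---|---|
| 07:00 | 8 h | 15.7% / 25.0% | 17 h | 2.0% / 5.3% |
| 08:00 | 7 h | 19.8% / 29.7% | 16 h | 2.5% / 6.25% |
| 09:00 | 6 h | 25.0% / 35.4% | 15 h | 3.1% / 7.4% |

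**At the next fasting reading.** This is 24 - 9 = 15 h after the evening dose, whatever the clock time. 0.5^(15/3) = 3.1% and 0.5^(15/4) = 7.4%.

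**Day 8.** Of the 24 h that Table 2 covers after this dose, 24 - 17 = 7 h to 24 - 15 = 9 h lie beyond the cut. A stop after Day 5, also a morning-only day, has the same timing.

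**Which events are caught.**

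1. A subject who goes on dosing is still within the treatment period, so overnight events on those nights stay on treatment. Only events starting after the final dose can be misplaced.
2. A second hypoglycaemia, or a single one difficult to cure, that starts after midnight and ends treatment is follow-up only. (Section 4.1.2 also discontinues a subject who needs rescue after the initial dose. Whether that reaches the night after Day 1 depends on how it is read, and nothing here relies on it.)
3. Fasting hyperglycaemia needs two consecutive mornings. If its onset is dated to the first, dosing was still under way and the overlap rule counts it on treatment as well. If it is dated to the second, it is follow-up only. The protocol does not fix the onset date.
4. For completers, an AE starting between midnight and the Day 9 assessment is follow-up only.

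**Size in the table.** 1/10 = 10 percentage points for one subject among the 10 planned, and slightly less if dropouts during titration enlarge the safety set. The shift arises only if the subject has no earlier on-treatment AE of the same term.

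**The case against.** The strongest reply is that the rule is explicit and reproducible and hides nothing. Section 13.2.4 also presents AEs over the whole study and has a separate category for those that ended treatment, and each AE carries its start, causality rating and action taken. This stands: the matter is one of labelling in one of several descriptive tables, and no inference rests on it.

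The reply also disposes of four stronger readings that a reader might infer:

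- **That a low fasting-morning reading by itself stops treatment.** The only stopping rule in Section 5.4.3 tied to that reading is hyperglycaemia on two mornings. Section 4.1.1 uses the reading to set the dose, and Section 4.1.2 answers a need for rescue during titration with a dose reduction.
- **That on-treatment hypoglycaemia is generally understated.** A subject stopped at a second episode will normally have had the first while still dosing. If that one was recorded as an AE, the on-treatment count of subjects with the term does not change.
- **That exposure is still substantial at the fasting reading or on the night after Day 8.** The 16-35% applies at midnight after an evening dose. At the fasting reading about 3-7% of parent remains, and at midnight on Day 8 about 2-7%.
- **That the Day 9 laboratory results move to follow-up.** Laboratory values are summarised by treatment and time, not by AE period. Under Section 7.3.3 a worsened protocol-mandated value becomes an AE only if it is serious or is the reason for stopping the drug, and the second cannot apply once the last planned dose has been given.

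It can also be said that 24 h is no more than a preference and that five half-lives would serve as well. That is fair as to the exact length. It does not defend a cut whose distance from the last dose ranges from 6 to 17 h according to which dose happened to be last.

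**Conclusion.** The point holds as a minor one of period attribution. Section 13.2.4 itself fixes a cut that assigns to follow-up any AE starting after midnight on the date of the final dose, and neither the extension nor the overlap sentence rescues it.

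It matters most after a final evening dose, and little for completers. The active metabolite would raise exposure at either cut, but by an amount the protocol does not allow one to state. The percentages rest on the assumed 07:00-09:00 morning dose, and on reading study drug in Section 13.2.4 as AZD1656. Section 6.4.3 lists metformin as an additional study drug, whereas Section 6.5 keeps the two apart.

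The documents do not support saying that events are lost, or that a 10-point shift is to be expected. That shift is the size of one event under the condition given above.

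**What to change.** In Section 13.2.4, define the on-treatment AE period as running from the first dose of AZD1656 to 24 h after the last dose of AZD1656, for completers and discontinued subjects alike, with follow-up starting thereafter. Name AZD1656 in place of the general term.

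A 24 h window covers the fasting reading 15 h after an evening dose. It exceeds five parent half-lives (5 x 3 = 15 h to 5 x 4 = 20 h) and matches the interval of Table 2 and AUC0-24. For an AE with a date but no time on the day the window closes (after discharge), state one convention.

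The cost is one sentence and one derivation, to be settled before clean file. No new data are needed: AE times are recorded during residence, drug administration is recorded in the CRF (Section 6.6), and the present rule already presumes a dosing time. No clinical procedure changes. The downside is that a few events move from follow-up to on treatment.
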